7.0 Research Plan and Procedures

7.1 This new consolidated section requests information about:

- Hypothesis
- Aims
- Study Design
- Background and Significance
- Preliminary Studies
- Procedures
- Statistical Methods
- References

Later sections include:

- Drugs and Devices
- Sample Size, Eligibility, and Subjects
- Recruitment and Consent
- Risks and Benefits
- Data and Safety Monitoring Plan
- Confidentiality, Privacy and Security
- Financial Considerations
- Qualifications of Personnel
- Other Approval and Registrations

7.2 HYPOTHESIS: Describe the hypothesis or what the study hopes to prove **(Help Text updated 9/13):**

We propose that patients with Polycystic Ovary Syndrome (PCOS) on a continuous 6 month active oral contraceptive (OCP) preparation (no placebo pills for 6 months straight) will have improved Testosterone suppression as compared to patients taking cyclical (monthly) OCPs, who may have rebound ovarian function during days 21-28 of their menstrual cycle when receiving sugar pills. With continuous OCP use we also hypothesize that patients will have improved clinical findings of hyperandrogenism (acne and hirsutism) compared to cyclic OCP users.

7.3 AIMS: List the specific aims:

1. To conduct a pilot feasibility study observing the use of 2 formulations of an OCP (continuous 168 day active hormone pills vs. cyclical 21 day active/7day placebo pill packs) in patients with Polycystic Ovary Syndrome (PCOS).
2. To determine the effect of 6 months of continuous (168 days of active hormone pills) vs. cyclical (21 day active and 7 day placebo pills) OCP therapy on biochemical findings of hyperandrogenism (Testosterone levels and free androgen index).
3. To determine the effect of 6 months of continuous (168 days of active hormone pills) vs. cyclical (21 day active/7 day placebo pills) OCP therapy on cutaneous findings of hyperandrogenism (male pattern hair growth also known as hirsutism and acne).
4. To determine the effect of 6 months of continuous (168 days of active hormone pills) vs. cyclical (21 day active/7 day placebo pills) OCP therapy on self reported symptoms of anxiety and /or depression as collected from validated questionnaires.

7.4 DESIGN: Briefly describe the study design (e.g., observational, interventional, randomized, placebo-controlled, blinded, cross-over, cross-sectional, longitudinal, pharmacokinetic, etc.):

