All potential participants in the study that go through the PCOS Multidisciplinary clinic have routine baseline blood work done (at least 1 month off any oral contraceptive pill) which includes total and free Testosterone levels, sex hormone binding globulin (SHBG), estradiol, luteinizing hormone (LH), follicle stimulating hormone (FSH), Hemoglobin A1c (HbA1c), insulin, fasting glucose, and a lipid panel. If baseline blood work is done > 2 months prior to enrollment, we will repeat these levels to ensure accuracy prior to start of study. As part of the clinic visit, patients routinely fill out a lengthy survey which includes a quality of life assessment and self-assessments regarding acne and hair growth. Potential participants will also have a routine initial dermatological exam to evaluate for hirsutism (using the modified Ferriman Gallwey aka mFG

score) and acne which takes place on their initial visit to clinic, prior to enrollment in the study. This information will all be included in the information gathered about each participant who enrolls in the study as it will provide baseline values.

All potential participants that present to the clinic for a reassessment will fill out a lengthy survey which includes a quality of life assessment and self-assessments regarding acne and hair growth. Potential participants will also have a routine initial dermatological exam to evaluate for hirsutism (using the modified Ferriman Gallwey aka mFG score) and acne which takes place on their initial visit to clinic, prior to enrollment in the study. This information will all be included in the information gathered about each participant who enrolls in the study as it will provide baseline values. If the potential participant still meets criteria for PCOS and meets criteria for the CCOUP study (see below), they will have routine baseline blood work done as a part of the study which includes total and free Testosterone levels, sex hormone binding globulin (SHBG), estradiol, luteinizing hormone (LH), follicle stimulating hormone (FSH), Hemoglobin A1c (HbA1c), insulin, fasting glucose, and a lipid panel.

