At 3 months into therapy, participants will come back to the PCOS clinic for routine care follow up and be seen by a Reproductive Endocrinology and Fertility specialist. This visit is considered routine and not specific to the study. However, during this visit a study investigator will also touch base briefly with the participants to see how they are doing. Four online surveys (through REDCap) will also be sent to participants that addresses if they have missed any doses of their medication, assess their quality of life, acne changes, screen for anxiety and depression. Patients will be asked to complete the BDI-II survey on their clinic day so that it can be evaluated by the study team immediately in the event that there are concerns for suicidal risk. In addition, participants will once again get blood work at their visit (including total Testosterone, SHBG, estradiol, LH, FSH) but will also go to their local lab (covered by their insurance) for additional routine labs including a fasting lipid panel, fasting serum glucose, insulin, and HbA1c. These labs are routinely done with follow up regardless of being in the study and should therefore be covered by each participant's insurance. Once again, the cyclical group should be on placebo/sugar pills at the time of blood draw and the continuous group on active hormone pills.

At 6 months into therapy, participants will come in for a study visit (this is not considered routine care) in which they will have their vitals taken, a physical exam that includes a re-evaluation of their mFG score, and an in-clinic pelvic ultrasound to assess ovarian volume and follicle counts performed by a Reproductive Endocrinology and Infertility specialist. They will also be emailed 5 post-study surveys through REDCap, that includes a quality of life questionnaire for PCOS, acne and hirsutism, as well as anxiety and depression screening, and includes questions regarding any missed doses of their medication. Patients will again be asked to complete the BDI-II survey on their clinic day so that it can be evaluated by the study team immediately in the event that there are concerns for suicidal risk. Lastly, participants will again have blood work drawn in the clinic (total Testosterone, SHBG, estradiol, LH, FSH). These labs are not considered standard of care and will be paid for by the study team.

Participants may also be called emailed reminders for follow up at least 2-3 times during the 6 month period.

CCOUP Study Timeline

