	Screening	Enrollment	1 month	3 months	(routine)
Questionnaires					
REDCap PCOS Multidisciplinary PCOS Clinic Pre-clinic Surveys (routine)	x				
REDCap Baseline Questionnaire		x			
REDCap 3 Month Follow Up Questionnaire /PCOS QOL				x	
REDCap 3 Month GAD-7 Questionnaire				x	
REDCap 3 month BDI-II Survey				x	
REDCap 3 Month Follow Up - Acne QOL Assessment				x	
REDCap 6 Month Follow Up Questionnaire /PCOS QOL					
REDCap 6 Month GAD-7 Questionnaire 2					
REDCap 6 Mond BDI-II Survey 2					
REDCap 6 Month Follow Up Questionnaire - Acne QOL Assessment					
REDCap 6 Month Follow Up Questionnaire - Hirsutism QOL Assessment					
Study Visits/Procedures					
Dermatologic Exam (mFG scoring)		x			
Pelvic Ultrasound		x			
Blood Work - Location	Patient's local lab - insurance covered	PCOS Clinic - study covers	PCOS Clinic - study covers	PCOS Clinic - study covers	Patient's local lab - insurance covered
Total Testosterone	x (routine)	*	†	†	
Free Testosterone	x (routine)	**			
Sex Hormone Binding Globulin	x (routine)	*	†	†	
LH	x (routine)	**	×		x
FSH	x (routine)	*	×		x
Estradiol	x (routine)	**	×		x
Fasting Lipid Panel	x (routine)	**			x
HbA1c	x (routine)	**			x
Fasting serum glucose	x (routine)	**			x
Insulin	x (routine)	**	†	†	
Email Reminders		x			x
* if initial screening blood work done at the patient's outside lab is obtained >2 months from start of study, these select labs will be sent from the PCOS clinic to the University of Virginia, Center for Endocrinology and Metabolism to establish accurate baseline values.					
** If the patient is a return patient to the clinic looking to reestablish care and participate with the study, all labs will be sent from the PCOS clinic to the University of Virginia, Center for Endocrinology and Metabolism to establish accurate baseline values.					
† indicates the select labs that will be sent from the PCOS clinic (where it is drawn) to the University of Virginia, Center for Endocrinology and Metabolism to establish accurate baseline values.					
Please refer to the attached study document "CCOUP Study Timeline" for the full procedure table.					

7.11 STANDARD CLINICAL PRACTICE: To what extent, if any, do the planned research procedures differ

from the care that people would otherwise receive at this institution or the study site if not being done locally:

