If the goal of therapy is management of hyperandrogenism and menstrual dysfunction, combined oral contraceptive pills (OCPs) are the mainstay of treatment based on *Endocrine Society* guidelines of PCOS. While there is no standard of care established regarding which combined OCP formulation and length of active pills that should be used in the treatment of women with PCOS, the mainstay of therapy has largely been monthly pill packs (21 days of active and 7 days of placebo pills) though continuous 3-6 month formulations have been used, with a 3rd or 4th generation progestin that provides some anti-androgen effect. Therapy with OCPs are individualized to each patient given the multitude of different formulations and their side effect profiles. In patients who have concerns for hirsutism an additional medication such as Spironolactone is often added to therapy. However, studies have shown that 4th generation progestins such as Drospirenone have a component of Spironolactone effect, limiting the need for dual therapy.

Comparatively, this study will use standard clinical practice guidelines in treating participants with an OCP that has a 4th generation progestin, Drospirenone. In addition, it is also standard clinical practice that patients seen at the PCOS Multidisciplinary clinic who are started on OCP therapy are followed up in 3 months for both a clinic visit and typically get routine blood work at this time as well.

Procedures that differ from the standard clinical practice in this study include: repeat blood work at 1 month and 6 months into OCP therapy, repeat pelvic ultrasound to assess ovarian volume and follicle counts at 6 months of therapy, and lastly a repeat modified Ferriman-Gallwey Hirsutism scoring done with a physical exam at the 6 month follow up.

7.12 INSTRUMENTS: List all questionnaires, surveys, interview, or focus group guides that will be used for this study:

	Screening	Enrollment	1 month	3 months	(routine)
Questionnaires					
REDCap PCOS Multidisciplinary PCOS Clinic Pre-clinic Surveys (routine)	x				
REDCap Baseline Questionnaire		x			
REDCap 3 Month Follow Up Questionnaire /PCOS QOL				x	
REDCap 3 Month GAD-7 Questionnaire				x	
REDCap 3 Month BDI-II Survey				x	
REDCap 3 Month Follow Up - Acne QOL Assessment				x	
REDCap 6 Month Follow Up Questionnaire /PCOS QOL					
REDCap 6 Month GAD-7 Questionnaire 2					
REDCap 6 Month BDI-II Survey 2					
REDCap 6 Month Follow Up Questionnaire - Acne QOL Assessment					

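### Acne is half of Aim 3, but the plan documents no acne measure taken the same way at baseline and at 6 months

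*Combined protocol and SAP*

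**What the plan says.** Section 7.3 of the combined protocol and SAP, Aim 3, sets out to compare the regimens on "cutaneous findings of hyperandrogenism (male pattern hair growth also known as hirsutism and acne". The hypothesis in 7.2 also names acne, and exclusion 3 in 9.8 treats cutaneous findings as a secondary outcome.

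At baseline, 7.10 describes a dermatological exam for hirsutism by mFG score "and acne which takes place on their initial visit to clinic, prior to enrollment in the study". It also describes "a lengthy survey which includes a quality of life assessment and self-assessments regarding acne and hair growth". Both are kept as baseline values. No acne grading scale is named, nor is the self-assessment instrument. The CCOUP Study Timeline adds a REDCap Baseline Questionnaire at enrolment, content not shown.

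At follow-up, the 6-month visit in 7.10 has "a physical exam that includes a re-evaluation of their mFG score". Section 7.11, on procedures beyond usual care, has "lastly a repeat modified Ferriman-Gallwey Hirsutism scoring done with a physical exam at the 6 month follow up". Section 13.6 mentions only hirsutism and the ovaries as being reassessed at study end. Section 16.3 lists a month-6 skin exam without saying what it covers. Acne on self-report appears as "REDCap 3 Month Follow Up - Acne QOL Assessment", with a 6-month counterpart; neither the Timeline nor the instrument list in 7.12 has a baseline row for that form.

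Section 7.26 gives no analysis for acne. Its baseline-adjusted ANCOVA is for metabolic parameters.

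**The concern.** Aim 3 is about a skin finding. The clinical measure of acne is described at the start and not at the end. The named acne questionnaire is listed after treatment has begun and not before. If staff follow the text, neither measure has a documented pair.

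Two things are at stake. First, what remains at 6 months is a quality-of-life score reported by participants who know their regimen. That is a different construct from a clinical acne finding, and it is open to expectation bias. Second, without a defined baseline on the same instrument, change in acne has no stated meaning, and the most useful covariate for the arm comparison may not be collected. A baseline that was not recorded cannot be recovered once treatment starts.

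**Working it through.** The plan states no figure for acne, and the 30 per arm in 9.1 and 9.3 is not based on power, so there is nothing to reproduce. The check is of the schedule, with an illustration of precision.

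**Step 1. Acne measures by time point, as documented.**

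| Measure | Baseline | 3 months | 6 months |
|---|---|---|---|
| Clinician exam of acne | Yes, no scale named (7.10) | Not described | Not described in 7.10, 7.11 or 13.6; skin exam of unstated scope in 16.3 |
| Acne QOL form | No row (Timeline, 7.12) | Listed | Listed |
| Other acne self-report | Yes, instrument unnamed (7.10); Baseline Questionnaire content not shown | None named | None named |

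No row is documented as the same measure at baseline and at 6 months.

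**Step 2. Could another acne form be hidden in the follow-up surveys?** Section 7.10 announces four surveys at 3 months. The rows are PCOS QOL, GAD-7, BDI-II and Acne QOL: four. It announces five at 6 months. The rows are those four plus Hirsutism QOL: five. The counts agree, so the Acne QOL is the only follow-up form that is named for acne. The open question lies at baseline. The 6-month column of the Timeline is not visible in the text available, and this check does not rely on it.

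**Step 3. What can be estimated.** Allocation is 1:1 at random (7.4), so the 6-month difference between arms in Acne QOL estimates an effect without any baseline. Change from 3 to 6 months can also be computed, but 3 months is after the start of treatment and is not a baseline.

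**Step 4. What a matching baseline adds.** With n per arm, outcome SD s and baseline-to-6-month correlation r:

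- no covariate: variance of the arm difference = 2s²/n
- ANCOVA on the matching baseline: 2s²(1 − r²)/n

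The documents give no r, so a range is assumed. For scale, also assume two-sided alpha 0.05, 80% power, no dropout and a normal approximation. With n = 30, the detectable difference without a covariate is (1.960 + 0.842) × √(2/30) = 2.802 × 0.2582 = 0.72 SD. The 95% interval half-width is 1.960 × 0.2582 = 0.51 SD. Multiplying 0.72 by √(1 − r²):

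| Assumed r | Variance left (1 − r²) | Reduction | Detectable difference |
|---|---|---|---|
| 0.3 | 0.91 | 9% | 0.69 SD |
| 0.5 | 0.75 | 25% | 0.63 SD |
| 0.7 | 0.51 | 49% | 0.52 SD |

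These compare with using no covariate. If the existing baseline acne data, with correlation q to the outcome, would otherwise be the covariate, the reduction is 1 − (1 − r²)/(1 − q²). For example, q = 0.3 and r = 0.5 give 1 − 0.75/0.91 = 18%, not 25%.

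**The case against.** A reader might infer that acne is examined only before enrolment, that change in acne cannot be estimated, and that half of Aim 3 is lost. The documents do not support readings that strong, for four reasons.

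- **The follow-up lists are not exhaustive.** Section 7.10 says what the 6-month exam includes, not all that it contains, and 7.11 omits vitals and surveys that 7.10 schedules. The skin exam in 16.3 is compatible with both and might cover acne. The Timeline's label for the dermatological exam mentions only mFG, yet the baseline exam also covers acne, so the label settles nothing.
- **Baseline self-report on acne exists.** The clinic survey and the Baseline Questionnaire could contain the Acne QOL items. The full procedure table is a separate attachment, so a gap in the available text is not proof of a gap in the plan.
- **Aim 3 asks for an effect between regimens, not for change from baseline.** Randomisation allows a 6-month comparison, and ANCOVA can adjust for a different baseline acne measure.
- **This is a pilot.** Its first aim is feasibility, and its sample size is not set by power.

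All four stand, and they narrow the point. They do not close it. None of the descriptions of the 6-month exam mentions acne, a payment line does not define a measurement, and no text says that the baseline items match the Acne QOL. A possible skin exam of unknown scope, with no scale, is not an outcome that can be analysed.

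**Conclusion.** The point holds in limited form. The plan documents no like-for-like acne measure at baseline and 6 months, and no clinical acne outcome at follow-up. It does allow an arm comparison of the Acne QOL at 6 months. That answers a patient-reported question in an open-label trial and leaves change from baseline undefined.

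The cost in precision is modest to moderate: 9% to 49% of the variance for assumed r of 0.3 to 0.7, as an upper illustration against no covariate, and less where existing baseline acne data predict the outcome. The larger cost is that the clinical half of the acne question may go unmeasured. The testosterone comparison is not affected. The change is worth making because it is cheap and serves a stated aim. The conclusion assumes that the separate procedure table and survey contents do not already fill the gap; if they do, 7.10 and 7.11 still need to say so.

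**What to change.** 1. In 7.10, 7.11 and the Timeline, name one clinical acne grade. The baseline exam names none, so this comes first. Record it at the baseline dermatological exam and again at the 6-month exam already scheduled for mFG. Make the skin exam in 16.3 refer to the same procedure.
2. Give the Acne QOL form at enrolment as well as at 3 and 6 months. If the baseline survey or the Baseline Questionnaire already contains it, say so instead.
3. In 7.26, state that the arms are compared at 6 months on each acne measure by ANCOVA on the matching baseline score.

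The cost is a minute or two at each exam and one short form, with no extra visit or staff. A clinical grade does not by itself remove bias from open-label assessment. Whether the examiner can be kept unaware of the regimen is a separate decision that the plan should record.

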REDCap 6 Month Follow Up Questionnaire - Hirsutism QOL Assessment					

Attach any unpublished instruments in the 'Other Study Documents' section of the Initial Review Submission Packet form after completing the study application. Published instruments should NOT be attached.

7.13 * BIOSPECIMEN COLLECTION: Are you drawing any blood or collecting other biosamples (e.g. tissue, buccal swabs, urine, saliva, hair, etc.): (REQUIRED)

Yes No

* Could this study generate genetic data that may be broadly shared (e.g., submitted to NIH in compliance with [Genomic Data Sharing \(GDS\)/Genome-Wide Association Studies \(GWAS\)](#) requirements): (REQUIRED)

Yes No

Please check the Resource Sharing Plan section of your funding notice. You will not be able to share the data as required by your funding agency if the consent form doesn't include the required language.

7.14 * TYPE OF SPECIMENS (check all that apply): (REQUIRED)

- Blood
- Tissue (describe below):
- Existing/archival materials (name source below): --
- Other (describe below):

7.15 * SPECIMENS ARE: (check all that apply): (REQUIRED)

- Leftover specimens from a clinical diagnostic or therapeutic procedure
- Specimens collected for research purposes only (including extra samples taken during a clinical procedure)
- Other

7.16 * DESTINATION: Specimens will ultimately be stored (check all that apply): (REQUIRED)

Outside Entity:

- Cooperative group bank
- NIH
- Other university
- Industry sponsor
- Other

Specify to what institution, cooperative group, or company specimens will be transferred:

Balancing cost and ease, a select few blood samples will be sent to University of Virginia, Center for Research in Reproduction (to test for testosterone, sex hormone binding globulin and insulin). During routine follow up at the 3 month check we expect participants will also get fasting blood work at their insurance-covered lab of their choice.

UCSF:

UCSF repository/bank being established under this protocol
 Existing UCSF specimen repository/bank with CHR approval
 Other location at UCSF (please describe)

Provide the name of the bank and iRIS approval number (if not being banked at UCSF under this protocol). If you checked 'Other,' please provide the location or lab:

Center for Reproductive Health
Reproductive Health Laboratories
[name]
[name]

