7.18 SPECIMENS SENT OUTSIDE UCSF - IDENTIFIABILITY: Will direct identifiers be associated with specimens or shared with other researchers and/or outside entities:

Yes
 No
 N/A - Specimens will not be shared with others

7.19 * FUTURE SPECIMEN USE: Will any specimens or portions of specimens be retained after the study is over for possible use in future research studies: (REQUIRED)

Yes No

7.21 * CLINICAL FOLLOW-UP DATA: Will clinical follow-up data be linked to specimens (i.e., will medical record information continue to be abstracted after the specimen is collected): (REQUIRED)

Yes No

Provide duration of follow-up or 'indefinitely':

7.26 STATISTICAL METHODS: Briefly summarize the methods and types of analyses that will be performed:

The means and standard deviation will be calculated for each of the blood tests within each treatment group and compared at the different time points to baseline measures. Additionally we will likely use a two sample t-test to estimate the difference in the mean Testosterone levels between the two treatment groups over the 6 month period. Analysis of covariance models, adjusted for the baseline measurement, will also likely be used to compare the treatment groups for metabolic parameters. Chi-Square analyses will be used to compare the treatment groups for reported anxiety and depression as analyzed categorically.

7.27 REFERENCES: List only the 5-10 most relevant references (a separate bibliography can be attached for reference purposes if this study involves novel approaches, agents, or an emerging technology that the IRB may not be familiar with):

3. The Rotterdam ESHRE/ASRM-Sponsored PCOS Consensus Workshop Group 2004 Revised 2003 consensus on diagnostic criteria and long-term health risks related to polycystic ovary syndrome. *Fertil Steril* 81:19-25.

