- Who is conducting the search for potential participants, and how?
- How are potential subjects being approached for recruitment? By whom, and when?

**If there will be more than one participant group (e.g. patients, healthy controls, caregivers, family members, providers, etc.), provide details about the recruitment plans for each group.
(Recommended length - 100-250 words)**

All new referrals sent to the UCSF PCOS Multidisciplinary clinic will be screened prior to their clinic visit by the clinical investigator(s), by reviewing APeX medical charts and REDCap database pre-clinic surveys that are routinely sent to patients prior to their first visit. There are 2 days each month in which the PCOS clinic sees new patients. Typically, at the first visit patients are evaluated by several multidisciplinary providers who come together at the end of the clinic day to discuss if the patient 1) meets criteria for the diagnosis of PCOS and 2) what medications or interventions they should be started on. At the second clinic visit, the same patients from earlier in the month are seen again for follow up to discuss the results of the previous visit and whether they will need to start any medication(s) or other therapeutic interventions.

All patients presenting for a PCOS re-evaluation will complete the same REDCap database pre-clinic surveys and routine labs as they would if they were presenting to the UCSF PCOS Multidisciplinary clinic. When they present for a reassessment, they will be seen for one visit in which they undergo the usual history and physical assessment. At the end of this evaluation, the patient will learn if they still meet criteria for PCOS and the medications or interventions they should be started on.

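### The sections disagree on which laboratory runs which blood test at which visit, so baseline and follow-up values can come from different labs for returning and for new patients

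*Combined protocol and SAP*

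**What the plan says.** Four parts of the application describe the laboratory for a returning (reassessment) patient's baseline.

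- Section 7.10, text: once she qualifies, "they will have routine baseline blood work done as a part of the study which includes total and free Testosterone levels". The list continues to ten items, with no laboratory named.
- Section 7.10, Timeline, footnote **: "all labs will be sent from the PCOS clinic to the University of Virginia, Center for Endocrinology and Metabolism". The ** mark stands in the Enrollment column, where the study pays, against free testosterone, LH, estradiol, lipids, HbA1c, glucose and insulin.
- Section 7.16: a small number of samples "will be sent to University of Virginia, Center for Research in Reproduction (to test for testosterone, sex hormone binding globulin and insulin". This is a different UVA centre from the one in the Timeline.
- Section 11.6: re-evaluation patients complete the same surveys and "routine labs as they would if they were presenting to the UCSF PCOS Multidisciplinary clinic". The Timeline places those routine labs at the patient's own insurance-covered lab.

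For month 3, the 7.10 text says that participants "will also go to their local lab (covered by their insurance) for additional routine labs including a fasting lipid panel", followed by glucose, insulin and HbA1c. The Timeline agrees for lipids, HbA1c and glucose. It marks insulin † at months 1 and 3, which means UVA. Total testosterone and SHBG are also † at both visits.

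Section 7.26 uses the baselines in two ways. Each blood test is summarised within arm and compared with baseline, and "Analysis of covariance models, adjusted for the baseline measurement, will also likely be used to compare the treatment groups for metabolic parameters".

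**The concern.** Both uses of the baseline in 7.26 assume that it is on the same scale as the follow-up value. Two laboratories can differ systematically on the same analyte. If the baseline comes from one and the follow-up from another, the change within an arm contains the lab difference as well as any drug effect. Site staff reading these sections cannot tell which route to use, and a pre-treatment sample that is misrouted cannot be replaced after the first pill. Section 9.3 opened enrolment to women who met PCOS criteria 2 to 10 years earlier because recruitment was slow, so the returning group may not be negligible. Its expected size is not given.

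**Working it through.** **Side-by-side reading of the routes**

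| Analyte | Returning woman, baseline | New patient, baseline | Follow-up |
|---|---|---|---|
| Lipids, HbA1c, glucose | UVA by footnote **; not on the 7.16 list | Local lab | Month 3: local lab |
| Insulin | UVA by footnote ** and 7.16 | Local lab | Month 3: local (7.10 text) or UVA (Timeline †) |
| Total testosterone, SHBG | UVA by footnote ** and 7.16 | Local lab if no more than 2 months old; otherwise UVA (footnote *) | UVA (†) |
| LH, FSH, estradiol | UVA by footnote **; not on the 7.16 list | Local lab (FSH at UVA under footnote * if the screening labs are older than 2 months) | Clinic draw in the 7.10 text; assaying lab not named |
| Free testosterone | UVA by footnote **; 7.16 says only testosterone | Local lab | None in the 7.10 text |

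Section 11.6, read with the Timeline's screening column, would move every entry in the returning column to a local lab.

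Of the ten baseline items, 7.16 covers three at UVA. That leaves 10 − 3 = 7 with no stated UVA assay, or 6 if testosterone there includes free testosterone.

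**Illustration of size**

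The documents give no returning share, lab difference or baseline-to-follow-up correlation. The following are assumptions: returning share f = 10% to 50%, lab difference d = 0.25 to 1.0 SD, correlation ρ = 0.6. The arm size of 30 is from section 9.1.

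1. Within-arm shift in mean change = f × d.
   - Smallest: 0.10 × 0.25 = 0.025 SD.
   - Middle: 0.25 × 0.5 = 0.125 SD.
   - Largest: 0.50 × 1.0 = 0.50 SD.
   - For scale, with equal variances the standard error of the mean change in one arm is √(2(1 − 0.6))/√30 = 0.163 SD.
2. ANCOVA precision. Mixing labs in the baseline weakens its correlation with follow-up to r = ρ/√(1 + f(1 − f)d²). The residual variance is multiplied by (1 − r²)/(1 − ρ²).
   - At f = 0.25 and d = 0.5: r = 0.6/√1.0469 = 0.586, and the ratio is 1.025.
   - Over the whole range the ratio runs from 1.003 to 1.113. The standard error rises by at most √1.113 − 1, about 5.5%.
3. ANCOVA bias. A simulation of 4,000 trials with 30 women per arm, f = 0.25, d = 0.5 and no true effect gave a mean between-arm estimate of −0.003 SD (Monte Carlo standard error 0.003). That is no detectable bias, as expected when entry route is independent of randomized arm.

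The formula in step 1 also applies to total testosterone and SHBG, with f now the share of an arm whose baseline is local and follow-up at UVA. The shift approaches the full lab difference as that share approaches one.

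**The case against.** The best defence is that this is a wording inconsistency in a 60-woman pilot, with little effect on what the trial is built to compare. Much of that stands. Arms are randomized, so the lab source is balanced between them on average. None of the four aims names a metabolic measure. For total testosterone and SHBG, the aim 2 measures, a returning woman whose baseline goes to UVA is the well-matched case. Section 7.26 specifies no test or significance level for the comparison with baseline. The extracted Timeline lacks its 6-month columns, and the attached full procedure table is not available here and might settle some entries.

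Two stronger readings are tempting. The documents support neither.

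- A reader might infer that returning women will have no metabolic baseline and will drop out of the ANCOVA. Sections 7.10 and 11.6 both promise them the panel. A baseline would be lost only if tubes were shipped under footnote ** to a laboratory that assays only the 7.16 list. That is an operational risk, not something the plan prescribes.
- A reader might infer that the treatment comparison is biased. It is not, for the reason given above.

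The defence does not remove the conflict between the current sections. Nor is the problem limited to returning women. A new patient with recent local results can have total testosterone and SHBG measured locally at baseline and at UVA afterwards. Nothing requires her to use the same local lab at baseline and month 3.

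**Conclusion.** The point holds as an inconsistency with a limited analytic cost. Sections 7.10, 7.16 and 11.6 do not assign one laboratory to each analyte and visit, and two UVA centres are named. Following footnote ** as written gives a returning woman lipid, HbA1c and glucose baselines from a different laboratory than her month-3 values. The harm falls on the within-arm comparison with baseline: f × d, or 0.025 to 0.50 SD over the assumed ranges. The ANCOVA's residual variance rises by 0.3% to 11% over the same ranges, with ρ = 0.6. These figures are illustrations only, because the share and the lab difference are unknown. The conflict itself rests on the text alone. The new-patient route for total testosterone and SHBG deserves equal attention, because it affects the aim 2 change from baseline.

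**What to change.** Replace footnote ** and make 7.10, 7.16 and 11.6 agree on one laboratory per analyte for baseline and follow-up, for new and returning women alike:

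- **Lipids, HbA1c, fasting glucose:** run before the first pill at the same local lab that will run that woman's month-3 panel.
- **Total testosterone, SHBG:** send the baseline sample to the UVA laboratory that runs the follow-up samples.
- **LH, FSH, estradiol:** name the laboratory that runs the follow-up samples, and run the baseline there.
- **Insulin:** resolve the month-3 conflict between the 7.10 text and the Timeline, then match the baseline to it.
- **UVA:** name one centre throughout.

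Section 12.6, which says no blood is collected in the clinic for the study or for recruitment, should be brought into line with the Enrollment draw.

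The cost is a wording amendment and a pre-treatment local draw for returning women. New patients whose recent local results would otherwise serve as baseline would also need an enrollment sample. The amendment must say who pays: the Timeline has the study covering the Enrollment draw, but local-lab work is insurance-covered. No additional participants are needed.
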